### 9.2. Analysis:

Objective 1: To demonstrate in a feasibility trial the optimal dose of losartan and effect size necessary to conduct a trial of losartan in participants with abnormal nocturnal dipping.

Objective 2: Demonstrate the Acceptability of and Barriers to Enrollment into a Feasibility Trial of Losartan.

Objective 3: Demonstrate and Promote Adherence to Study Medication during Feasibility Trial

Objective 4: Demonstrate Adherence to Study Procedures and Retention in the Clinical Trial.

Analysis for Objective 1: The feasibility trial will evaluate two dosing strategies of losartan. The DSMB will be instrumental in evaluating safety of losartan during the course of the trial. At the end of the trial, the two dosing strategies for losartan will be directly compared using student's t-test. The effect size necessary to conduct a definitive trial will be obtained through identifying the acceptance rate (objective 2), adherence/dropout rate (objective 3 and 4). The correction of abnormal nocturnal dipping will be evaluated using

continuous data. To properly power a definitive trial, this feasibility trial will document the standard deviation/variability in BP among participants, the estimated difference in nocturnal blood pressure at baseline and exit.

Analysis for Objective 2: The acceptance rate will be defined by the percent of participants enrolled divided by the number of patients approached for enrollment. The acceptability of the trial will be defined by evaluating barriers or facilitators to enrolling in this feasibility trial. Dichotomous dependent variables will be created for participants that enroll or do not enroll in the study. Independent variables will reflect (ordinal) responses provided during the survey. Bivariate relationships will be tested using chi-square or Fischer's exact tests and/or logistic regression. The mentorship team will review the identified barriers and facilitators to enrollment and develop strategies to enhance enrollment in future BP trials. For example, if mistrust is a barrier, a future strategy enrollment may include peer-delivered video testimonials.

Analysis for Objective 3. [name] will mentor [name] in the analysis of medication adherence during a clinical trial. Specifically, the adherence rates will be reviewed for each individual participant and for all participants over time to determine feasibility of losartan adherence over the six month trial. In addition, the effect of adherence interventions (calendar, phone calls) on losartan will be reviewed as well as participant reasons stated for good/poor adherence. The mentoring team will review adherence reports and work to develop an intervention plan for enhanced adherence during the planned definitive trial.

Analysis for Objective 4: To effectively design a multicenter trial, it is vital to understand the rate and barriers to trial retention and feasibility of repeated ABPM prior to conducting a SCD hypertension trial. The retention rate will be recorded and re-evaluated against the initial Likert surveys to identify variables that may suggest future drop-out. The completion of ABPM at baseline, 3 months, and 6 months will be recorded, including days to return ABPM device. [name] will mentor [name] in analyzing the barriers in a hypertension trial.

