## 9. SAMPLE SIZE AND STATISTICAL ANALYSIS

### 9.1 Sample Size

An endpoint for this feasibility trial is to determine the effect size needed to appropriately power a definitive trial of losartan to correct nocturnal dipping, rather than efficacy of losartan. Data will be collected to understand the acceptance rate, rate of recruitment, and the drop-out rate. In preliminary fashion this feasibility trial will identify the difference in nocturnal BP improvement between the two treatment arms, and within group standard deviation of BP. The feasibility trial will evaluate the change in nocturnal dipping % from baseline in all participants and among participants receiving two different dosing strategies (intensive losartan therapy (BP <75th percentile) as compared to standard dosing (BP <95th percentile)). Sample size analysis for repeated measures and adjustments to sample size to compensate for non-adherence will occur.

The feasibility trial will enroll 40 participants with hypertension (clinic and ABPM). It is expected that 30% of the 200 cohort participants will meet eligibility criteria. Of these 60 cohort participants, we expect that 40 participants will enroll in the feasibility trial. We expect a dropout rate of <10% to ensure that the feasibility trial has > 30 participants, an accepted participant size for feasibility trials.

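### Section 9.2 takes the definitive trial's effect size from acceptance and adherence/dropout rates, and the difference and SD named for powering are of blood pressure, not dipping %

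*Combined protocol and SAP*

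**What the plan says.** Section 9.1 makes the effect size for a definitive losartan trial in nocturnal dipping an endpoint, and disclaims efficacy. It will evaluate "change in nocturnal dipping % from baseline in all participants and among participants receiving two different dosing strategies". The quantities it names are "difference in nocturnal BP improvement between the two treatment arms, and within group standard deviation of BP". It adds that "Sample size analysis for repeated measures and adjustments to sample size to compensate for non-adherence will occur".

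Section 9.2, Objective 1, says:
- For the arms, "the two dosing strategies for losartan will be directly compared using student's t-test". No outcome, time point or covariate is named.
- On the effect size: "The effect size necessary to conduct a definitive trial will be obtained through identifying the acceptance rate (objective 2), adherence/dropout rate".
- On the outcome: "The correction of abnormal nocturnal dipping will be evaluated using" continuous data.
- To power the definitive trial, the study will "document the standard deviation/variability in BP among participants, the estimated difference in nocturnal blood pressure at baseline and exit".

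Under Objective 4, "The completion of ABPM at baseline, 3 months, and 6 months will be recorded". This is the only use of the 3-month recording in section 9.

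Section 4.3 defines dipping as the awake mean minus the sleep mean, divided by the awake mean, times 100. Section 2.2 specifies an intention-to-treat analysis. Section 2.2.d admits participants on systolic or diastolic dipping below 10%, or on abnormal nocturnal load. Section 6.3 titrates the dose on clinic blood pressure.

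**The concern.** There are two separate faults in what Objective 1 hands to the next trial.

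First, the stated source of the effect size is wrong. A standardised effect needs a mean difference and an SD of one outcome. Acceptance and dropout inform accrual and the inflation of N. Non-adherence can dilute an intention-to-treat difference. None of these rates can produce the effect size.

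Second, the target is dipping %, a ratio of two means, but the difference and SD listed for powering are in mm Hg. Treatment guided by clinic pressure may lower awake and sleep pressure together. That lowers nocturnal pressure but leaves the ratio almost unchanged, so a nocturnal-pressure difference and SD cannot stand in for the dipping ones. Systolic or diastolic is not specified either. Nor is the within-person correlation, which a repeated-measures sample size needs, listed for reporting.

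The quantity at stake is one that the trial names as its own deliverable: section 1.1.b lists sample size calculations for a phase III trial among the objectives.

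**Working it through.** **The plan's own numbers.** 200 × 0.30 = 60 eligible; 40 enrolled (40/60 = 66.7% acceptance); 40 × 0.90 = 36, which exceeds 30. These reproduce. There is no power calculation to check. With 1:1 allocation (assumed, as the ratio is not stated), 36 gives 18 per arm.

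**Does a nocturnal-pressure difference convert to dipping %?** The formula is from section 4.3. The pressures are assumed, starting at 120/114 mm Hg, and sleep pressure falls by 6 in every row.

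| Awake fall (mm Hg) | Awake/sleep after | Dip | Change in dip |
|---|---|---|---|
| baseline | 120/114 | 6/120 = 5.00% | – |
| 6 | 114/108 | 6/114 = 5.26% | +0.26 |
| 3 | 117/108 | 9/117 = 7.69% | +2.69 |
| 0 | 120/108 | 12/120 = 10.00% | +5.00 |

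One nocturnal difference is compatible with very different dipping differences.

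**Would baseline adjustment help?** Set the follow-up SD to 1. Let k be the ratio of baseline to follow-up SD and r the baseline-to-6-month correlation. Both are assumed, because the documents give neither.
- Change score: V = 1 + k² − 2rk; half-width = 2.032 × √(2V/18), on 34 df.
- Adjusted: V = 1 − r²; half-width = 2.035 × √(2V(1 + 1/32)/18), on 33 df. The factor 1 + 1/32 allows for chance baseline imbalance.
- N per arm: two-sample t-test, illustrative difference of 0.5 follow-up SD, 80% power, two-sided 5%. The adjusted N uses V = 1 − r².

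| k | r | Half-width, change | Half-width, adjusted | Adjusted vs change | N per arm, change | N per arm, adjusted |
|---|---|---|---|---|---|---|
| 1 | 0.3 | 0.802 | 0.657 | 18.0% narrower | 89 | 59 |
| 1 | 0.5 | 0.677 | 0.596 | 12.0% narrower | 64 | 49 |
| 1 | 0.7 | 0.525 | 0.492 | 6.3% narrower | 39 | 34 |
| 0.8 | 0.3 | 0.730 | 0.657 | 10.0% narrower | 74 | 59 |
| 0.8 | 0.5 | 0.621 | 0.596 | 3.9% narrower | 54 | 49 |
| 0.8 | 0.7 | 0.488 | 0.492 | 0.7% wider | 34 | 34 |
| 0.6 | 0.3 | 0.677 | 0.657 | 3.0% narrower | 64 | 59 |
| 0.6 | 0.5 | 0.591 | 0.596 | 1.0% wider | 49 | 49 |
| 0.6 | 0.7 | 0.488 | 0.492 | 0.7% wider | 34 | 34 |

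Entry requires a repeat abnormal recording, so a narrow baseline SD (k below 1) is plausible.

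**Could adherence be counted twice?** If non-adherers gained nothing (assumed), 10% or 20% non-adherence shrinks an intention-to-treat difference to 0.9 or 0.8 of full. N then rises by 1/0.9² = 1.23 or 1/0.8² = 1.56. If the observed difference already contains this dilution, applying the section 9.1 adjustment again would overstate N by the same factors.

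**The case against.** Several counter-arguments stand.

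- **The t-test is valid.** Section 9.1 speaks of change from baseline, so the test may be on change scores and would then already use baseline. A reader might infer bias from the lack of adjustment. The documents do not support that: the arms are randomised, and the only possible gain is precision.
- **Dipping data will exist.** Section 9.1 plans dipping change overall and by arm, and section 4.3 records the calculation. It would be too strong to say that the trial cannot deliver a dipping effect size. What is missing is a line saying that the dipping difference and SD are what is handed on.
- **Recording nocturnal pressure is legitimate.** Sections 2.2.b and 2.2.d also admit participants on nocturnal load, although section 6 mentions dipping only.
- **The comparator of the definitive trial is not stated.** The arm difference may not be its only input, so the all-participant change that section 9.1 plans belongs in the report too. Both arms receive losartan, so that change is a before-after quantity.
- **The effect-size sentence may be loose drafting.** The same paragraph goes on to list an SD and a difference for powering. That limits the harm, but those are in BP, so the paragraph does not correct itself.
- **Precision stays poor either way.** Adjusted half-widths of 0.49 to 0.66 SD are close to or above the illustrative 0.5 SD. Sampling error in the variance (34 df) alone multiplies N by 0.65 to 1.72.

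**Conclusion.** The point holds on two matters of text. The effect-size sentence is wrong as written. The difference and SD named for powering are also not on the outcome that the definitive trial is meant to target. Both fall within the trial's stated purpose, so they should be corrected, and the feasibility label does not excuse them.

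The ratio between the 0.26-point and 5.0-point results might be read as the size of the plan's error. It is not: the pressures are assumed, and the example shows only that one scale does not determine the other.

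Baseline adjustment is the minor part. With 18 per arm, correlations of 0.3 to 0.7 and SD ratios of 0.6 to 1, all assumed, the interval runs from 18% narrower to 1% wider than a change score. The gain may be nil.

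**What to change.** 1. Reword the effect-size sentence in section 9.2. The effect size comes from the difference and SD of dipping %; acceptance and dropout inform accrual and inflation of N. State whether the non-adherence adjustment in section 9.1 is applied to an intention-to-treat difference that already contains dilution.
2. Name systolic or diastolic dipping % at 6 months as the variable. On it, report the all-participant change from baseline, the between-arm difference with 95% CI, the SD and the baseline-to-follow-up correlation. Report nocturnal blood pressure separately, with its own difference and SD.
3. As a low-cost improvement, estimate the arm difference by a linear model adjusted for baseline dipping %, in place of the unadjusted t-test. Adjusting the change score for baseline gives the same arm difference, so the change outcome in section 9.1 can stay. A mixed model of months 3 and 6 is optional. It would keep participants who have a 3-month but no 6-month recording, under a missing-at-random assumption.

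Cost: wording only, since every value is already collected. Item 3 uses one degree of freedom (t from 2.032 to 2.035) and slightly more analysis work, and may widen the interval by about 1%.

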### 1.1.b Secondary Objectives

Objective 1: To determine the acceptability of enrollment and retention in a randomized feasibility trial of losartan

Objective 2: To determine the safety of losartan at two different dosing strategies

Objective 3: To complete the necessary preparations for a definitive phase III trial including preparing a manual of operations, case report forms, and sample size calculations

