## 2.2.b. Inclusion Criteria for Feasibility Trial Screening

1. Enrolled in Pediatric Cohort Study
2. History of abnormal clinic blood pressure (3 abnormal blood pressure readings (systolic or diastolic) in last 4 visits) as defined by NHLBI Blood Pressure Tables for age and height.
3. History of 1) abnormal nocturnal blood pressure dipping as defined by <10% dip (daytime-nighttime systolic or diastolic blood pressure/daytime blood pressure x 100) or 2) abnormal nocturnal load defined by >25% sleep BP >95th percentile.
4. Informed consent in accordance with the institutional policies (institutional IRB approval) and Federal guidelines (approved by the United States Department of Health and Human Services) must be signed by the participant's legally authorized guardian acknowledging written consent to join the study

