## 6. LOSARTAN DOSING AND MONITORING

Prior to randomization, participants will need to have 1) three documented blood pressure recordings (in last 4 visits) documenting a systolic or diastolic blood pressure that is >95th percentile for age, gender, and height as defined by NHBLI BP tables and 2) two 24 hour ABPM recordings documenting abnormal nocturnal blood pressure dipping.

6.1. Initial Dose: All participants will be initiated on 25 mg of losartan at their initial monthly visit.

6.2. Randomization scheme.

This trial will use block randomization with 6 participants per block. The blocks will be put in sealed envelopes and seven blocks out of 10 possible blocks will be selected by the pharmacist. Participants assigned A will receive intensive dosing of losartan (titrate

to keep BP <75th percentile) and B will receive standard dosing of losartan (titrate to keep BP <95th percentile).

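### The baseline-to-exit blood pressure change is listed as an input for powering the definitive trial, but it is uncontrolled and may carry regression to the mean

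*Combined protocol and SAP*

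**What the plan says.** Section 9.1 sets out two kinds of quantity. One is a change over time: "The feasibility trial will evaluate the change in nocturnal dipping % from baseline in all participants", and also by dosing strategy. The other is a randomised contrast: "the difference in nocturnal BP improvement between the two treatment arms, and within group standard deviation of BP". Under Objective 1, section 9.2 says that "the two dosing strategies for losartan will be directly compared using" Student's t-test, without naming the outcome variable. It then lists what will be documented to power a definitive trial, including "the estimated difference in nocturnal blood pressure at baseline and exit". Secondary Objective 3 (1.1.b) makes this planning role explicit: "To complete the necessary preparations for a definitive phase III trial including preparing a manual of operations, case report forms, and sample size calculations".

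There is no untreated arm. Section 6.1 reads "All participants will be initiated on 25 mg of losartan at their initial monthly visit", and the arms differ only in the clinic BP target.

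Entry depends on abnormal ABPM results. Section 6 asks for "two 24 hour ABPM recordings documenting abnormal nocturnal blood pressure dipping". Sections 2.2.b and 2.2.d also accept a second route, "abnormal nocturnal load defined by >25% sleep BP" above the 95th percentile in 2.2.b, and 2.2.d requires the repeat recording to be abnormal before randomization. Section 2.3.a, on baseline evaluations, lists that repeat under its screening step and no ABPM under its randomization step. Section 2.2 speaks only of a baseline ABPM and the schedule table only of one at Entry. No sentence says which recording is the analysis baseline.

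**The concern.** A recording that had to be abnormal for the participant to be randomised is, on average, abnormal partly by chance. The next recording will look better even if the drug does nothing. Requiring two abnormal recordings weakens this effect but does not remove it, because the second recording is itself selected. If the second recording is the baseline, the pooled baseline-to-exit change contains drug effect plus drift, and with no untreated arm the study cannot separate them. The plan contains no correction.

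This matters because planning a later trial is a stated product of the study. If that trial has a no-losartan control, the before-after change is the only estimate of losartan's effect that this study gives, and an inflated value makes the later trial too small. If it compares dosing strategies, the before-after change is the wrong input and the arm difference is the right one.

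**Working it through.** **1. The plan's own figures.** Section 9.1 gives recruitment arithmetic only: 200 × 0.30 = 60 eligible, of whom 40 enrol; at 10% dropout, 40 × 0.90 = 36 remain, above the required 30. This reproduces. The documents give no effect size, SD, power or ABPM reliability, so every input below is assumed.

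**2. Drift with no drug effect.** Each recording's dip is a stable personal value plus independent occasion error. Assumed: mean dip 10%, SD 5 or 6 points, test-retest correlation 0.5; awake systolic BP mean 120 or 126, SD 10, correlation 0.5 or 0.7; sleep 95th percentile 115 or 120; within-night SD 9. A load above 25% then means a sleep mean above the 95th percentile minus 0.674 × 9 = 6.1 mmHg. Participants are kept if dip is below 10% or load is above 25% on both recordings (the wider rule of 2.2.b and 2.2.d, systolic only). The mean change from the second qualifying recording to a later one is:

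| Dip SD | Drift in dip (points) |
|---|---|
| 5 | about 0.7 to 1.2 |
| 6 | about 0.9 to 1.6 |

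The ranges cover the eight combinations of awake BP and percentile settings. Over a wider grid (mean 8 to 12, correlation 0.3 to 0.7) the drift is 0.3 to 3.0 points. If a separate recording after eligibility is the baseline, the drift is about zero. The difference between randomised arms is also about zero, because both arms drift equally. Selection on clinic BP and on diastolic load is not modelled.

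**3. Consequence if the later trial has a no-losartan control.** Two-sample t-test, two-sided 5%, 80% power, SD 5. The normal approximation is n per arm = 2 × [(1.96 + 0.84) × 5 / effect]²; the t-based answer is slightly larger.

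- True effect 2: 2 × (14.0/2)² = 98; t-based 100 per arm.
- Planning effect 2 + 1.5 = 3.5: 2 × (14.0/3.5)² = 32; t-based 34 per arm.
- Power of 34 per arm for a true effect of 2: standard error 5 × √(2/34) = 1.21 and 2/1.21 = 1.65, which gives 37%.

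A drift of 1.5 is near the top of the illustrative range. At 0.7 the planning effect is 2.7, the plan is 55 per arm, and power is 55%.

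**4. Precision of the arm difference.** Take 20 per arm, SD 5, and a correlation r of 0.20 to 0.64 between baseline and 6 months (the range among selected participants over the wider grid). The 95% half-width is t × SD × √(2/20), where √(2/20) = 0.316.

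| Analysis | SD used | Half-width |
|---|---|---|
| t-test on 6-month values | 5 | 2.02 × 5 × 0.316 = 3.2 |
| t-test on change | 5 × √(2(1 − r)) = 6.3 to 4.2 | 4.0 to 2.7 |
| ANCOVA | 5 × √(1 − r²) = 4.9 to 3.8 | 3.1 to 2.5 |

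**The case against.** The strongest reply is that the plan already has the right estimate. Section 9.1 plans the between-arm difference, says that the aim is an effect size and not efficacy, and calls the work preliminary. It says only that the pooled change will be evaluated; it does not name that change as a powering input. This stands. Only the 9.2 phrase is tied to powering, and alone it could mean the arm difference at each time point. The reference in 9.1 to all participants supports the within-participant reading but does not prove it.

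It is also fair that the baseline is open. Entry could be a randomization visit separate from screening, and then the drift vanishes. Against this, the randomization step in 2.3.a lists no ABPM. The enrollment survey's count of further recordings does not decide the matter, because it fits either reading depending on when the survey is completed.

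A reader might infer that the plan commits to an inflated losartan effect, or that the definitive trial will be underpowered. The documents support neither. They do not define the baseline, do not state the later trial's comparator, and give no variability from which to size the bias. Nor is the t-test invalid: the randomised comparison is unbiased with or without adjustment, and ANCOVA is a gain in precision.

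**Conclusion.** The point holds in a conditional form. Section 9.2 puts a baseline-to-exit difference among the powering inputs, with no untreated arm and no caution. If the phrase means within-participant change, it is uncontrolled. If the baseline is also the qualifying repeat, it is biased towards improvement. That direction follows from the design; the size does not. The drift of 0.7 to 1.6 dip points is an illustration under assumed inputs. The comparison of 34 with 100 per arm also needs a no-losartan control in the later trial, which the documents do not mention. These figures are for dipping %, whereas the quoted phrase concerns nocturnal BP. This is a cheap improvement; the randomised comparison needs no rescue.

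**What to change.** 1. In 9.1 and 9.2, add: 'The pooled change from baseline to 3 and 6 months is descriptive and will not be used unadjusted as the effect size for a definitive trial.'
2. In 9.2, replace the unadjusted Student's t-test with ANCOVA of the 6-month value on arm and baseline value. Report the intensive-versus-standard difference with its 95% confidence interval as the planning input for a trial that compares strategies.
3. In 2.3.a and the schedule table, state whether the analysis baseline is the qualifying repeat ABPM. This sentence alone would not be enough; it makes items 1 and 2 unambiguous.

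Items 1 to 3 are wording changes and use recordings already scheduled. ANCOVA costs one degree of freedom, and the losartan effect that can be quoted becomes smaller and less precise. Only if a separate baseline recording is chosen is there a further cost: 40 × $25 = $1,000 in family payments (section 11), plus shipping and analysis, for which the documents give no amount.
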